5.1 Inclusion criteria

Subjects are eligible to be included in the study only if all of the following inclusion criteria apply:

Informed consent

1 Capable of giving signed informed consent which includes compliance with the requirements and restrictions listed in the ICF and in this CSP.

Paediatric cohort: parent/legal guardian consent is required, where possible involving the paediatric subject in the assent process with appropriate documentation.

2 Provision of signed and dated written ICF prior to any mandatory study-specific procedures, sampling, and analyses.

Paediatric cohort: mandatory provision of signed and dated parent/legal guardian consent for the study along with the paediatric assent form, when applicable. For subjects who reach the age of legal consent during the clinical study, notification may be required and a new consent form may need to be signed by the subject.

The ICF process is described in Appendix A 3.

Age

3 Paediatric cohort: Chinese subjects ≥3 years and <18 years of age with a BSA ≥0.55 m² at the time of study enrolment who are able to swallow whole capsules. There must be a

CONFIDENTIAL AND PROPRIETARY 42 of 183

minimum of 6 subjects each in the 3 to 11 and 12 to 17 year age groups at the time of enrolment.

Adult cohort: Chinese subjects ≥ 18 years of age at the time of study enrolment who are able to swallow whole capsules.

Disease diagnosis

- 4 All study subjects must be diagnosed with (i) NF1 per NIH Consensus Development Conference Statement 1988 and (ii) inoperable PN. In addition to PN, subjects must have at least 1 other diagnostic criterion for NF1 (NIH Consensus Development Conference Statement 1988):
- Six or more café-au-lait macules >5 mm in greatest diameter in pre-pubertal individuals and >15 mm in greatest diameter in post-pubertal individuals.
- Freckling in the axillary or inguinal regions.
- Optic glioma.
- Two or more Lisch nodules (iris hamartomas).
- A distinctive osseous lesion such as sphenoid dysplasia or tibial pseudarthrosis.
- A first-degree relative with NF1.

A PN is defined as a neurofibroma that has grown along the length of a nerve and may involve multiple fascicles and branches. A histologic confirmation of the tumour is not necessary in the presence of consistent clinical and radiographic findings, but should be considered if malignant degeneration of a PN is clinically suspected.

Inoperable PN is defined as PN that cannot be completely surgically removed without a risk of substantial morbidity due to encasement of, or close proximity to, vital structures, invasiveness, or high vascularity of the PN.

- 5 Subjects' NF1 and inoperable PN require treatment due to actual symptoms or has the potential to develop significant clinical complications, as judged by the investigator, including but not limited to head and neck lesions that could compromise the airway or great vessels, paraspinal lesions that can cause myelopathy, brachial or lumbar plexus lesions that could cause nerve compression and loss of function, lesions that could result in major deformity (e.g. orbital lesions) or are significantly disfiguring, lesions of the extremity that cause limb hypertrophy or loss of function, and painful lesions.
- 6 Subjects must have at least one measurable typical or nodular PN, defined as a lesion of at least 3 cm measured in one dimension, which can be seen on at least 3 imaging slices and have a reasonably well-defined contour. Subjects who have undergone surgery for resection of a PN are eligible provided the PN was incompletely resected and is measurable. The target PN will be defined as the clinically most relevant PN, which has to be amenable to volumetric MRI analysis and classified as either typical or nodular (ie must not be solitary nodular).

CONFIDENTIAL AND PROPRIETARY 43 of 183

- 7 Performance status: Subjects >16 years of age must have a Karnofsky performance level of ≥70, and children ≤16 years old must have a Lansky performance of ≥70 (Appendix G). Subjects who are wheelchair bound because of paralysis secondary to a PN should be considered ambulatory when they are in their wheelchair. Similarly, subjects with limited mobility secondary to a need for mechanical support (such as an airway PN requiring tracheostomy or continuous positive airway pressure) will also be considered ambulatory for the purpose of the study.
- 8 Adequate haematological function defined as absolute neutrophil count $\geq 1.5 \times 10^{9}/L$, haemoglobin $\geq 9g/dL$, and platelet count $\geq 100 \times 10^{9}/L$. Subject must be without growth factor support and platelet transfusion support 7 days before the screening assessment.
- 9 Adequate organ function defined as follows: aspartate aminotransferase (AST) and alanine aminotransferase (ALT) ≤2×upper limit of normal (ULN), total bilirubin ≤1.5×ULN except in the case of subjects with documented Gilbert's disease (≤2.5×ULN). Estimated creatinine clearance of ≥60 mL/minute, calculated using the formula of Cockcroft and Gault ([140 minus age] mass [kg]/[72 creatinine mg/dL] multiply by 0.85 if female) or normal serum creatinine based on age, as described below:

Age (years)	Maximum creatinine (mg/dL)	Maximum creatinine (µmol/L)
≤5	0.8	70.7
5 <age≤10< td="">1.0	88.4	</age≤10<>	1.0	88.4
10 <age≤15< td="">1.2	106.1	</age≤15<>	1.2	106.1
>15	1.5	132.6

Reproduction

- 10 Negative pregnancy test (urine or serum) for female subjects of childbearing potential. A female of childbearing potential is defined as a subject 9 years of age and older or those showing pubertal development.
- 11 Female subjects with childbearing potential must be 1 year post-menopausal (amenorrhoeic for the past 12 months without an alternative medical cause), surgically sterile, or using an acceptable method of contraception for the duration of the study (from the time of signing consent) and for at least 4 weeks after the last dose of selumetinib to prevent pregnancy. An acceptable method of contraception is a combination of 2 methods, including but not limited to implants, injectables, combined oral contraceptives (e.g. the contraceptive pill), some intrauterine devices (e.g. placement of an intrauterine device or intrauterine system), and a male partner with sterilisation. True sexual abstinence is also an acceptable method of contraception. Reliable methods of contraception/birth control should be used consistently and correctly. The following age-specific requirements must also apply:

CONFIDENTIAL AND PROPRIETARY 44 of 183

- Women <50 years old would be considered post-menopausal if they have been amenorrhoeic for the past 12 months or more following cessation of exogenous hormonal treatments. The levels of luteinising hormone and follicle-stimulating hormone must also be in the post-menopausal range.
- Women ≥50 years old would be considered post-menopausal if they have been amenorrhoeic for the past 12 months or more following cessation of all exogenous hormonal treatments, have had radiation-induced oophorectomy with the last menses >1 year ago, have had chemotherapy-induced menopause with >1 year interval since the last menses, or have had surgical sterilisation by either bilateral oophorectomy or hysterectomy.
- 12 Male subjects of reproductive potential must be surgically sterile by prior vasectomy or using an acceptable method of contraception (including use of condoms with spermicidal foams/gels or true abstinence) for the duration of the study (from the time they sign consent) and for at least 12 weeks after the last dose of study treatment to prevent pregnancy in a partner. Male subjects must not donate or bank sperm during this same time period.

5.2 Exclusion criteria

Subjects are eligible to be included in the study only if none of the following exclusion criteria apply:

- 1 Evidence of malignant peripheral nerve sheath tumour.
- 2 Prior malignancy (except for adequately treated basal cell or squamous cell skin cancer, in situ cervical cancer, or other cancer from which the subject had been disease free for ≥2 years or which would not have limited survival to <2 years) or other cancer requiring treatment with chemotherapy or radiation therapy. Note: these cases must have been discussed with the study physician.

- 3 A life-threatening illness, medical condition, or organ system dysfunction which, in the investigator's opinion, could compromise the subject's safety, interfere with the absorption or metabolism of selumetinib, or put the study outcomes at undue risk.
- 4 Subjects with clinically significant cardiovascular disease as defined by the following:
- Known inherited coronary disease;
- BP:
 - For paediatric subjects, BP > the 95th percentile for age, height, and gender measured as described in (Appendix F).
 - Uncontrolled hypertension (at screening: BP \geq 150/95 despite optimal therapy).
- Acute coronary syndrome within 6 months prior to starting treatment;

- Uncontrolled angina Canadian Cardiovascular Society grade II to IV despite medical therapy (Appendix F);
- Symptomatic heart failure New York Heart Association Class II to IV, prior or current cardiomyopathy, or severe valvular heart disease (Appendix F);
- Prior or current cardiomyopathy including but not limited to the following:
 - Known hypertrophic cardiomyopathy.
 - Known arrhythmogenic right ventricular cardiomyopathy.
 - Previous moderate or severe impairment of LVEF <45% on echocardiogram or equivalent on multigated acquisition (MUGA) even if full recovery has occurred.
- Baseline LVEF below the LLN or <55% measured by echocardiogram or institution's LLN for MUGA;
- Severe valvular heart disease;
- Current or history of atrial fibrillation ;
- QT interval corrected by Fridericia's method (QTcF) >450 ms or other factors that increase the risk of QT prolongation.
- 5 Known history of human immunodeficiency virus, serologic status reflecting active hepatitis B virus (HBV) or hepatitis C virus (HCV) infection, or any uncontrolled active systemic infection:
- Subjects who are hepatitis B core antibody positive and who are surface antigen (HBsAg) negative will need to have a negative HBV deoxyribonucleic acid polymerase chain reaction (PCR) result before enrolment. Subjects who are HBsAg positive or hepatitis B PCR positive will be excluded;
- Subjects who are hepatitis C antibody positive will need to have a negative HCV ribonucleic acid PCR result before enrolment. Those who are hepatitis C PCR positive will be excluded.
- 6 Subjects with the following ophthalmological findings/conditions:
- Current or past history of retinal pigment epithelial detachment/central serous retinopathy or retinal vein occlusion;
- Intraocular pressure >21 mmHg (or ULN adjusted by age) or uncontrolled glaucoma (irrespective of IOP). Subjects with known glaucoma and increased IOP who do not have meaningful vision (light perception only or no light perception) and are not experiencing pain related to the glaucoma, may be eligible after discussion with the study physician.
- Any other significant abnormality on ophthalmic examination that would make the subject unsuitable for enrolment into the study, as assessed by the investigator.

- Ophthalmological findings secondary to long-standing optic pathway glioma (such as visual loss, optic nerve pallor or strabismus) or longstanding orbito-temporal PN (such as visual loss, strabismus) will NOT be considered a significant abnormality for the purposes of the study.
- 7 Have received or are receiving an investigational medicinal product (IMP) or other systemic PN target treatment (including chemotherapy, hormonal therapy, radiation therapy, immunotherapy or biologic therapy) within 4 weeks prior to the first dose of study treatment, or within a period during which the IMP or systemic PN target treatment has not been cleared from the body (e.g. a period of 5 'half-lives'), whichever is the most appropriate and as judged by the investigator.
- 8 Inability to undergo MRI and/or contraindication for MRI (i.e. prosthesis or orthopaedic or dental braces that would interfere with volumetric analysis of target PN on MRI).
- 9 Have refractory nausea and vomiting, chronic gastrointestinal diseases (e.g. inflammatory bowel disease), or significant bowel resection that would adversely affect the absorption/bioavailability of the orally administered study medication.
- 10 Have had prior treatment with a MEK, Ras or Raf inhibitor (including, but not limited to, vemurafenib).
- 11 Supplementation with vitamin E greater than 100% of the daily recommended dose. Any multivitamin containing vitamin E must be stopped prior to initiation of selumetinib.
- 12 Receiving herbal supplements or medications known to be strong inhibitors or inducers of the cytochrome P450 (CYP)2C19 and CYP3A4 enzymes unless such products can be safely discontinued at least 14 days before the first dose of study medication.
- 13 Have any unresolved chronic toxicity *except alopecia* with Common Terminology Criteria for Adverse Events (CTCAE) grade ≥2, from previous anticancer therapy including radiation.
- 14 Have had recent major surgery within a minimum of 4 weeks prior to starting study treatment, with the exception of surgical placement for vascular access. Have planned major surgery during the treatment period.
- 15 Known severe hypersensitivity to selumetinib or any excipient in the selumetinib formulation, or history of allergic reactions attributed to compounds of similar chemical or biologic composition to selumetinib.
- 16 Breastfeeding or pregnant (it is allowed to discontinue lactation and participate in the study; however, resumption of lactation after study completion is not allowed).
- 17 Have evidence of any other significant clinical disorder or laboratory finding that, as judged by the investigator, makes it undesirable for the subject to participate in the study.
- 18 Judgment by the investigator that the subject should not participate in the study if the subject is unlikely to comply with study procedures, restrictions and requirements.

CONFIDENTIAL AND PROPRIETARY 47 of 183

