AE=adverse event; anti-HBc=hepatitis B core antibody; BP=blood pressure; C=cycle; DNA=deoxyribonucleic acid; ECG=electrocardiogram; EORTC QLQ-C30=European Organisation for Research and Treatment of Cancer Quality of Life Questionnaire Core 30; EoT=end of treatment; FLACC=Face, Legs, Activity, Cry, Consolability; HBsAg=hepatitis B surface antigen; HBV=hepatitis B virus; HCV=hepatitis C virus; NA=not applicable; NRS=Numeric Rating Scale; PCR=polymerase chain reaction; PedsQL=Paediatric Quality of Life Inventory; PGIC=patient's global impression of change; PGIS=patient's global impression of severity; PII=Pain Interference Index; PK=pharmacokinetics; PlexiQoL=plexiform neurofibromas quality of life scale; PROMIS=Patient-Reported Outcomes Measurement Information System; RNA=ribonucleic acid.

^a Assessments will be performed at the end of each cycle. Selumetinib will be dispensed after all assessments have been performed and the next cycle will begin at that point.

- ^b Screening tests should be performed within 28 days before the first administration of study treatment, unless otherwise indicated.
- ^c Treatment with selumetinib may be continued until disease progression or unacceptable drug-related toxicity, whichever occurs first.
- ^d The EoT visit will be performed for subjects who permanently discontinue study treatment for any reason (except for death, lost to follow-up or withdrawal of consent).
- ^e The 30-day safety follow-up assessments will be conducted at 30 days post-last dose/EoT for both paediatric and adult cohorts.
- ^f Long-term post-treatment safety follow-up assessments will be conducted for 1 year (at 6 and 12 months post-treatment) for paediatric subjects only.
- ^g Subjects need to be hospitalised for intensive PK sampling during the single dose period (from Cycle 0 Day -1 to Cycle 0 Day 2) and on Cycle 1 Day 8. During Cycle 0, PK samples will be collected pre-dose, 30 minutes, and 1, 1.5, 3, 6, 8, 12, 24 and 30 hours post-dose. At Cycle 1 Day 8, PK sample time points will be collected pre-dose, 30 minutes, and 1.5, 3, 6, and 12 hours post-dose.
- ^h Subjects who are anti-HBc positive and who are HBsAg negative will need to have a negative HBV DNA PCR result before enrolment.
- ⁱ Subjects who are hepatitis C antibody positive will need to have a negative HCV RNA PCR result before enrolment.

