- ^j Assessments will be performed at screening and at the end of each cycle up to the end of Cycle 4, every 2 cycles up to the end of Cycle 12, every 4 cycles up to the end of Cycle 24, and every 6 cycles thereafter, as long as the subject remains on study treatment. Assessments may also be performed at other visits during Cycles 0 and 1, as detailed. Screening assessments are suggested to be performed as close to Cycle 0 Day 1 and within 14 days.
- ^k Pregnancy testing will be performed at screening, Cycle 0 Day 1 and at the end of each cycle in women of childbearing potential only (see Section 5.1) and more frequently, if clinically indicated. A urine or serum pregnancy test is acceptable. Screening assessments are suggested to be performed as close to Cycle 0 Day 1 and within 14 days.
- ¹ The complete physical examination includes an assessment of the following: general appearance, respiratory, cardiovascular, abdomen, skin, head and neck (including ears, eyes, nose and throat), lymph nodes, thyroid, musculoskeletal (including spine and extremities) and neurological systems.
- ^m Axillary temperature, pulse rate, oxygen saturation by pulse oximetry, respiratory rate, and BP will be assessed. Assessments of BP and pulse rate should be assessed in a sitting position and preceded by at least 5 minutes of rest in a quiet setting without distractions (e.g. television, cell phones). Manual techniques will be used only if automated devices are not available.
- ⁿ Height and weight measurements will be performed in light clothing and with shoes off.
- ^o Subjects should be supine and at rest 5 minutes prior to recording the ECG.
- ^p The subject should be examined using the same machine and operator throughout the study wherever possible.
- ^q Ophthalmologic assessments may be performed more often, if clinically indicated.
- ^r An x-ray will be performed at screening and at other visits/cycles, if clinically indicated.
- ^s AEs will be collected from the time of signing the informed consent form, throughout the treatment period, and including the follow-up period.

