- ^t Tumour assessments will be performed at screening and every 4 cycles (16±1 weeks) up to the end of Cycle 24 (i.e. at the end of Cycles 4, 8, 12, 16, 20, and 24). From the end of Cycle 24, tumour assessments will be performed every 6 cycles (24±1 weeks) as long as the subject remains on study treatment or until disease progression. Subjects who discontinue study treatment due to reasons other than disease progression will continue to undergo tumour assessments for approximately 1 year, if clinically applicable, and the assessment schedule should continue per the regular tumour assessment interval.
- ^u Disfigurement assessments will be performed at screening and at the end of Cycles 8, 16 and 24 as long as the subject remains on study treatment.
- ^v Baseline clinical outcome assessments should be performed prior to and as close to the first dose of selumetinib as possible (PGIC should not have any baseline assessments). Post-baseline assessments should be performed at the end of each cycle up to the end of Cycle 4, every 2 cycles up to the end of Cycle 12, every 4 cycles up to the end of Cycle 24, and every 6 cycles thereafter, as long as the subject remains on study treatment. In the pediatric cohort, the pain medication survey will be completed on paper by the parent. In the adult cohort, the pain medication survey will be completed on paper by the patients. Other assessments will be performed electronically using on-site tablets.

- * Adults and children from 8 to 17 years of age will complete self-reported PII; parents/legal guardian of children from 5 to 17 years of age will complete the parent proxy PII.
- Subject-reported versions are for subjects aged 5 to 7 years, 8 to 12 years, and 13 to 17 years. In addition, the corresponding parent-reported versions will also be included. For subjects 3 to 4 years of age, only the parent-reported version will be included.
- ^y Self-reported short forms will be administered to children from 8 to 17 years of age and parallel parent proxy forms to children aged from 5 to 17 years. In the adult cohort, a newly developed PROMIS short form physical functioning scale will be used.
- ^z Will be parent-reported for children aged up to 17 years and self-reported for children aged 8 to 17 years and adults.

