All screening evaluations must be completed and reviewed to confirm that potential subjects meet all of the eligibility criteria. The investigator will maintain a screening log to record details of all screened subjects and to confirm eligibility or record the reasons for screening failure, as applicable.

Procedures conducted as part of the subject's routine clinical management (e.g. blood count) and obtained before signing of the ICF may be utilised for screening or baseline purposes provided the procedures met the protocol-specified criteria and were performed within the time frame defined in Table 1.

Repeated or unscheduled samples may be taken for safety reasons or due to technical issues with the samples.

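### The intervals after surgery and prior PN therapy are counted to the first dose, not to the baseline MRI, so a baseline volume may be measured 0 to 1 day after a partial PN resection

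*Protocol*

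**What the plan says.** **Intervals before treatment (Protocol 5.2; Table 6).** Exclusion 14 applies to subjects who "Have had recent major surgery within a minimum of 4 weeks prior to starting study treatment". Exclusion 7 covers another investigational product or systemic PN-targeted treatment, radiation included. Its 4-week interval is also "within 4 weeks prior to the first dose of study treatment". The alternative is a clearance period, for example 5 half-lives, "whichever is the most appropriate and as judged by the investigator". Table 6 counts to the same point.

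**Baseline MRI (Protocol 1.1, Table 1).** Footnote b: "Screening tests should be performed within 28 days before the first administration of study treatment, unless otherwise indicated". Footnote t: "Tumour assessments will be performed at screening and every 4 cycles"; it sets no tighter pre-dose limit. The 14-day advice, "Screening assessments are suggested to be performed as close to Cycle 0 Day 1 and within 14 days", is in footnotes j and k. The tumour assessment row carries only footnote t.

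**Resected tumours (Protocol 5.1, criterion 6).** "Subjects who have undergone surgery for resection of a PN are eligible provided the PN was incompletely resected and is measurable". No interval between resection and MRI is given.

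**Routine-care scans (general text on procedures printed after the Section 7.3 heading).** Procedures from routine management "obtained before signing of the ICF may be utilised for screening or baseline purposes", if they meet the protocol's criteria and fall inside the Table 1 window.

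**Use of the baseline.** Section 9.5 takes the most recent pre-dose assessment as baseline. Section 8.1.1 defines PR as a fall of at least 20% in target PN volume from baseline. PD is a rise of at least 20% from baseline or, after a PR, from best response.

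**The concern.** The exclusion intervals and the MRI window are about equally long and end at the same point, so they can overlap completely. A subject can satisfy every criterion and still have the baseline volume measured almost immediately after an operation on the target PN. If that volume includes transient swelling, its disappearance by the first on-study scan is recorded as shrinkage.

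The protocol's safeguards do not catch this. Confirmation 3 to 6 months later compares with the same baseline volume. Independent central review reads the same baseline image. There is no control arm in which the artefact would also appear. The rule that the most recent pre-dose assessment is the baseline helps only if a second pre-dose MRI is taken, and none is required.

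At stake are ORR, BOR, percentage volume change and any progression measured from baseline.

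**Working it through.** The plan states no figure for this interval, so there is none to reproduce. The check is calendar arithmetic plus the algebra of the response threshold.

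**1. Interval to the baseline MRI**

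Inputs: a 4-week (28-day) interval to first dose (exclusions 7 and 14); MRI between Day -28 and Day -1 (Table 1). Let *m* be the days from MRI to first dose. The last permitted event is 28 or 29 days before first dose, depending on whether an event exactly 4 weeks earlier is excluded.

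Shortest interval = 28 - *m* to 29 - *m*

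| MRI on | Shortest interval (days) |
|---|---|
| Day -28 | 0 to 1 |
| Day -21 | 7 to 8 |
| Day -14 | 14 to 15 |
| Day -7 | 21 to 22 |
| Day -1 | 27 to 28 |

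If the same 4 weeks were counted to the MRI, the shortest interval would be about 28 days on every row.

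**2. Swelling needed to meet PR**

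Let *b* be the transient inflation of the true baseline volume and *t* the true later change.

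Apparent change = (1 + *t*) / (1 + *b*) - 1

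PR needs this to be -0.20 or lower, so *b* must be at least (1 + *t*) / 0.8 - 1.

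| True change *t* | Inflation *b* needed |
|---|---|
| 0 | 25% |
| -5% | 18.75% |
| -10% | 12.5% |
| -15% | 6.25% |

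Inflation of 25% of the true volume is 0.25 / 1.25 = 20% of the measured volume. The documents give no size for post-operative swelling, so *b* is an assumption throughout.

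**3. Progression measured from baseline**

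With *b* = 12.5% and no true shrinkage, resolution gives 1 / 1.125 - 1 = -11.1%, which is not a PR. Baseline then remains the reference for progression. PD requires 1.125 × 1.20 = 1.35 times the true volume, so true growth of 35% rather than 20%.

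**4. Carry-over from prior therapy**

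If earlier treatment is still shrinking the PN at baseline, the bias is towards PR. If it has suppressed the volume by a fraction *s* that later reverses, the apparent change is 1 / (1 - *s*) - 1. With *s* = 16.7% this is +20%, an apparent PD. The direction is therefore not fixed.

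**5. Scale in a cohort of 16 (Section 9.2)**

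One false PR adds 1/16 = 6.25 points. For illustration, 10/16 = 62.5% (Clopper-Pearson 95% CI 35.4 to 84.8) becomes 11/16 = 68.8% (41.3 to 89.0). As a check on the interval code, the 33/50 = 66% cited in Section 2.2 returns the stated 51.2 to 78.8.

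**The case against.** The strongest reply is that nothing here contradicts itself. Exclusions 7 and 14 are eligibility rules anchored to treatment, and neither claims to govern imaging.

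The surgical route also needs several things together: a PN resection near the eligibility boundary, an MRI soon after it, that PN chosen as target, and swelling that is large enough. Section 2.2 says that only a few patients eventually receive surgery. Inclusion 6 requires a reasonably clear contour, visibility on at least 3 slices and suitability for volumetric analysis, which some immediately post-operative lesions may fail. The MRI acquisition protocol and the site imaging guideline are not at hand and may address recent surgery.

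On prior therapy, Section 2.2 reports moderate to no activity for earlier systemic treatments, and exclusion 10 bars previous MEK, Ras or Raf inhibitors. Finally, ORR is secondary and no hypothesis is tested (Section 9.1).

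Most of this stands, and it limits how far the point reaches. A reader might infer any of the following, and the documents support none of them:

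- **That false responses are to be expected.** No passage gives the number of recently operated subjects or the size of any swelling. The number affected may be zero.
- **That prior therapy would create false PRs.** The effect can go either way, and the protocol's own account suggests that it would be small.
- **That every tumour endpoint rests on this one volume.** After a PR, Sections 7.1 and 8.1.1 also measure progression from best response, and that comparison does not involve the baseline volume.
- **That exclusion 7 should require the longer of its two periods.** That would alter an eligibility and clearance rule and would not move the MRI.

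The replies do not close the timing gap. The inclusion 6 image conditions concern whether a lesion can be measured, not whether its volume is stable. A routine post-operative scan inside the window can serve as baseline.

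**Conclusion.** The gap is real on the text: the protocol allows 0 to 1 day between a partial PN resection or prior PN therapy and the baseline MRI, and no stated safeguard corrects a distorted baseline. The consequence is a potential bias, not an error in a stated figure. It bears on ORR, BOR, percentage volume change and progression measured from baseline, but not on progression measured from best response after a PR.

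The size is 6.25 points of a cohort's ORR per affected subject, given swelling of 25% of true volume with no true shrinkage, or 12.5% with 10% shrinkage. Those percentages are assumptions. Exclusion 14 reaches PN resection only where it counts as major surgery. Because the endpoint is secondary and descriptive and the number affected may be zero, this is a worthwhile low-cost improvement and does not undermine the study's primary objectives.

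**What to change.** In Table 1 footnote t, cross-referenced from exclusions 7 and 14, state that the MRI used as baseline must be acquired after the protocol's already stated surgery and prior-therapy intervals have elapsed. Leave the lengths of those intervals, and the wording "whichever is the most appropriate and as judged by the investigator" in exclusion 7 with its counterpart in Table 6, unchanged. The change concerns only when the measurement is taken.

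For subjects already enrolled, list the interval from the last PN surgery or PN-directed therapy to the baseline MRI, and repeat ORR without those whose interval was shorter than stated. If there are none, the listing shows that ORR is unaffected.

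Cost: a wording change, one listing and one sensitivity estimate. For a few subjects the MRI would be booked late in screening, or screening would start later.
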